6.3. Primary and Secondary Analyses

6.3.1. Primary Efficacy Analyses

The primary objective in Part A is safety (Section 6.4).

The primary efficacy assessment in Part B is the proportion of subjects who achieve an ACR20 response. To meet the ACR20 response, a subject must have at least 20% improvement from baseline in the following ACR core set components:

- TJC (68 joint count)
- SJC (66 joint count)
- At least 3 of the following 5 assessments:
 - 1) Physician's Global Assessment of Disease Activity (0-100 mm visual analog scale [VAS])
 - 2) Patient's Global Assessment of Disease Activity (0-100 mm VAS)
 - 3) Patient's assessment of pain (0-100 mm VAS)
 - 4) Patient's assessment of physical function as measured by the Health Assessment Questionnaire-Disability Index (HAQ-DI)
 - 5) Acute phase reactant as measured by hsCRP

Calculate ACR response (Responder, Non-responder, or Missing) at a visit will follow this algorithm:

Parameter	Abbreviation for the Parameter
% improvement in tender joint count	TJC68
% improvement in swollen joint count	SJC66
% improvement in Physician's Global Assessment of Disease Activity	PHYGA
% improvement in Patient's Global Assessment of Disease Activity	PATGA
% improvement in patient's assessment of pain	PATPain
% improvement in HAQ-DI	HAQ
% improvement in hsCRP	hsCRP

For all 7 parameters mentioned above, % improvement at a visit is calculated as:

$$(\text{baseline value} - \text{value at visit}) * 100 / \text{baseline value}.$$

Step 1: If the subject discontinued from the study prior to reaching a visit, assign ACR20 as Missing.

Otherwise, go to Step 2.

Step 2: If both TJC68 and SJC 66 are nonmissing and $\geq 20\%$, then go to Step 3. Otherwise,

If either TJC68 or SJC66 is nonmissing and $< 20\%$, then assign ACR20 as Non-Responder.

If both TJC68 and SJC66 are missing OR either TJC68 or SJC66 is nonmissing and the nonmissing value is $\geq 20\%$, then assign ACR20 as Missing.

Step 3: Consider the remaining 5 variables: PHYGA, PATGA, PATPain, HAQ, and hsCRP.

If ≥ 3 variables are missing, then assign ACR20 as Missing.

Otherwise, then proceed with the following order:

If ≥ 3 variables are $\geq 20\%$, then assign ACR20 as Responder.

If ≥ 3 variables are $< 20\%$, then assign ACR20 as Non-Responder.

If < 3 variables are $\geq 20\%$, then assign ACR20 response as Missing.

The number and percentage of subjects achieving ACR20 response over time will be summarized by treatment group.

The primary endpoint in Part B will be analyzed by a logistic regression model with ACR20 at Week 12 as the dependent variable and treatment, region (Japan versus non-Japan), biologic DMARD experience (yes/no), and baseline DAS28-hsCRP as independent variables using the mITT population. The comparison of each LY3337641 dose to placebo will be presented. The logistic regression model will test the treatment difference between each LY3337641 dose and placebo in the proportion of subjects achieving ACR20 at Week 12 using the Wald test at a 2-sided significance level of 0.05. The NRI method as described in Section 6.1.3.1 will be used to impute missing data.

6.3.2. Additional Analyses on the Primary Efficacy Measure

The ACR20 in Part A will be derived using ACR core set components and follow the algorithm in Section 6.3.1. Each component of the ACR20 (ie, TJC, SJC, Physician’s Global Assessment of Disease Activity, Patient’s Global Assessment of Disease Activity, patient’s assessment of pain, HAQ-DI, and hsCRP) and ACR20 in Part A will be summarized over time by treatment.

The primary endpoint in Part B will also be analyzed by a logistic regression model with ACR20 at Week 12 as the dependent variable and treatment, region (Japan versus non-Japan), biologic DMARD experience (yes/no), and baseline DAS28-hsCRP as independent variables using the per-protocol population as a sensitivity analysis. Each component of the ACR20 (ie, TJC, SJC, Physician’s Global Assessment of Disease Activity, Patient’s Global Assessment of Disease Activity, patient’s assessment of pain, HAQ-DI, and hsCRP) will be summarized over time by treatment. The change from baseline will be analyzed by a maximum-likelihood-based mixed model repeated measures (MMRM) analysis of covariance (ANCOVA). The change from baseline for each component of the ACR20 to each scheduled postbaseline time point is the dependent variable in the model. Baseline, treatment, region (Japan versus non-Japan), week of treatment (categorical), the interaction of treatment and week, biologic DMARD experience (yes/no), and baseline DAS28-hsCRP are fixed effects; subject and error are random effects. The covariance structures to be tested in this model include unstructured covariance, compound symmetry (CS), heterogeneous CS, heterogeneous autoregressive (AR1), or heterogeneous Toeplitz. The best covariance structure will be selected based on the Akaike’s Information Criterion (AIC). The Kenward-Roger approximation will be used to estimate the denominator degrees of freedom. Type III tests for the least squares mean (LSMean) will be used for the statistical comparison; the 95% CI will also be reported.

6.3.3. Secondary Analyses

6.3.3.1. ACR50, ACR70, ACR90, ACRN, and Hybrid ACR

The ACR50, ACR70, ACR90 responses are calculated as improvements of at least 50%, 70%, and 90% respectively. The data in Part B will be summarized and analyzed using the same method as for the primary efficacy endpoint (ie, ACR20).

ACRN is a continuous measure of percentage improvement from baseline in American College of Rheumatology criteria: this index is defined operationally as the lowest of either (a) the percentage change in TJC, (b) the percentage change in SJC, or (c) the median percentage change in the remaining 5 ACR core criteria (eg, a subject with an ACR-N of “X” has improvement of at least “X%” in tender and swollen joints and a median improvement of at least “X%” in the 5 remaining ACR core criteria). The ACRN will be summarized by treatment and each scheduled postbaseline time point. The ACRN at each scheduled postbaseline time point in Part B will be analyzed by MMRM ANCOVA. Treatment, region (Japan versus non-Japan), week of treatment (categorical), the interaction of treatment and week, biologic DMARD experience (yes/no), and baseline DAS28-hsCRP are fixed effect and subject and error are random effect.

The hybrid ACR (bounded) response measure will be obtained as described by the ACR Committee to Reevaluate Improvement Criteria (Felson et al. 2007) which has been provided in [Table JPDA.6.2](#).

Table JPDA.6.2. Scoring Method for the Hybrid American College of Rheumatology Response Measure

ACR Status	Mean % Change in Core Set Measures			
	<20	≥20, <50	≥50, <70	≥70
Not ACR20	Mean % Change	19.99	19.99	19.99
ACR20 but not ACR50	20	Mean % Change	49.99	49.99
ACR50 but not ACR70	50	50	Mean % Change	69.99
ACR70	70	70	70	Mean % Change

Abbreviations: ACR = American College of Rheumatology; ACR20 = 20% improvement in ACR criteria; ACR50 = 50% improvement in ACR criteria; ACR70 = 70% improvement in ACR criteria.

Scoring Method:

- 1) Calculate the average percentage change in core set measures. For each core set measure, subtract score after treatment from baseline score and determine percentage improvement in each measure. Next, if a core set measure worsened by >100%, limit that percentage change to 100% (set equal to -100% bound). Then, average the percentage changes for all core set measures.
- 2) Determine whether the subject has achieved ACR20, ACR50, or ACR70.
- 3) Using the table above, obtain the hybrid ACR response measure. To use the table, take the ACR20, ACR50, or ACR70 status of the subject (left column) and the mean percentage improvement in core set items; the hybrid ACR score is where they intersect in the table.

Note: Component-level imputation will be performed for the calculation of hybrid ACR. If at least 1 of the 7 core set measures is nonmissing at the visit and the subject is still enrolled in the study, then use last observation carried forward (LOCF) to fill in any missing values. These imputed values will be used to calculate the average percentage change in 7 core set measures and to calculate ACR20, ACR50, and ACR70.

Source of table and 1-3 steps: Felson et al. 2007.

The Hybrid ACR response will be summarized by treatment at all postbaseline visits. The Hybrid ACR response at each scheduled postbaseline visit in Part B will be analyzed using the Wilcoxon rank-sum test controlled by biologic DMARD experience (yes/no) and baseline DAS28-hsCRP categories (≤ 5.1 / > 5.1). The median difference of the change from baseline score and its 95% CI will be estimated by the Hodges-Lehmann method. The mLOCF approach will be used to impute missing data.

Note: Week 12 is the secondary analysis time point and all other time points are exploratory. ACR90 and ACRN are for the exploratory analyses.

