5.2. Determination of Sample Size

Approximately 32 at least mildly active RA subjects will be enrolled and randomly assigned in a 1:1:1:1 ratio to 1 of the 3 doses of LY3337641 (5, 10, or 30 mg) or placebo in Part A. This sample size is customary for evaluating safety and PK and/or PD parameters, and is not powered on the basis of statistical hypothesis testing.

Approximately 244 moderately to severely active RA subjects will be enrolled and randomly assigned in a 1:1:1:1 ratio to 1 of the 3 doses of LY3337641 (5, 10, or 30 mg) or placebo in Part B. All subjects who discontinue the treatment early (before Week 12) will be considered as failing the primary endpoint in Part B. The sample size of 61 subjects per arm will provide at least 80% power at the 2-sided .05 significance level to detect a difference of 25% in the primary endpoint (ACR20 response rate at Week 12) between each LY3337641 dose and placebo, assuming a 30% placebo response rate.

If the assessment committee determines that a dose adjustment is needed, the total study sample size may be adjusted.

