6.1. General Statistical Considerations

Statistical analysis of this study will be the responsibility of Eli Lilly and Company or its designee.

This plan describes a priori statistical analyses for safety, efficacy, and health outcomes data that will be performed.

In general, continuous variables will be summarized including number of observations, mean, standard deviation (SD), minimum, median, and maximum values. Categorical variables will be presented as counts and percentages. Data from Part A will be summarized separately from data from Part B. No statistical hypothesis testing is planned for Part A. All tests of treatment effects in Part B will be conducted at the 2-sided α level of .05, unless otherwise stated. No adjustments for multiplicity will be performed.

Unless otherwise specified, statistical analyses to compare treatment groups will use statistical techniques with treatment group and randomization strata [ie, biologic DMARD experience (yes/no), region (Japan versus non-Japan), and baseline DAS28-hsCRP (continuous)] as factors. In addition, for analysis of continuous measures, the baseline value of the dependent variable will be included as a covariate. Fisher's exact test will be used for the analysis of categorical measures unless otherwise specified.

P-values from statistical tests of treatment effects in safety analyses should be interpreted with caution as the analyses are intended to be descriptive and should not be considered as formal hypothesis testing. P-values and confidence intervals (CIs), if reported, provide some evidence of the strength of the finding.

For the purpose of presentation, the treatment groups of Parts A and B will be assigned by randomized treatment, and the treatment groups of Follow-up period will be assigned by the last used treatment.

The analyses for the optional long-term extension is described in Section [6.5.5](#).

Additional exploratory analyses of the data will be conducted as deemed appropriate.

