6.3.3.2. DAS28-hsCRP

The DAS28-hsCRP is a measure of RA disease activity in 28 joints that consists of a composite numerical score of the following variables: TJC, SJC, hsCRP (mg/L), and the Patient's Global Assessment of Disease Activity (Vander Cruyssen et al. 2005).

$$DAS28 - hsCRP = 0.56(\sqrt{TJC28}) + 0.28(\sqrt{SJC28}) + 0.36[\ln(CRP + 1)] + 0.014(VAS) + 0.96$$

DAS28-hsCRP will be summarized by treatment at each postbaseline visit. If hsCRP is missing at a postbaseline visit, the previous postbaseline hsCRP value will be carried forward and will be used to calculate DAS28-hsCRP. The change from baseline in DAS28-hsCRP to each scheduled postbaseline time point in Part B will be analyzed by the MMRM ANCOVA. Baseline, treatment, region (Japan versus non-Japan), week of treatment (categorical), the interaction of treatment and week, biologic DMARD experience (yes/no), and baseline DAS28-hsCRP are fixed effects; subjects and error are random effects.

Subjects with DAS28-hsCRP <2.6 will be considered as having achieved clinical remission; the criterion for achieving low disease activity (LDA) will be DAS28-hsCRP ≤3.2. The number and percentage of subjects who achieve clinical remission or LDA overtime will be summarized separately and analyzed using method similar to the primary analysis.

The number and percentage of subjects with DAS28-hsCRP <2.6, ≥2.6 to ≤3.2, >3.2 to ≤5.1, >5.1 in Part B will also be summarized. The treatment group difference compare to placebo will be assessed using a Cochran-Mantel-Haenszel test, adjusting for biologic DMARD experience (yes/no), and baseline DAS28-hsCRP category (≤5.1/>5.1).

Assessments of subjects with RA by EULAR response criteria (Table JPDA.6.3) will be used to categorize subjects as nonresponders, moderate responders, good responders, or responders (moderate + good responders) according to van Gestel et al. 1998.

The number and percentage of Part B subjects in each category [nonresponders, moderate responders, good responders, or responders (moderate + good responders)] will be summarized. The treatment group will be compared to placebo using a Cochran-Mantel-Haenszel test, adjusting for biologic DMARD experience (yes/no), and baseline DAS28-hsCRP category (≤5.1/>5.1).

Table JPDA.6.3. European League Against Rheumatism Response Criteria

Postbaseline level of DAS28-hsCRP	DAS28-hsCRP improvement		
	>1.2	>0.6 and ≤1.2	≤0.6
≤3.2	Good Response	Moderate Response	No Response

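### The Wald logistic test specified for ACR70 and ACR90, and by natural reading for remission, has no fallback for an arm without responders: an empty placebo arm gives p near 1 for all three doses

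*SAP*

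**What the plan says.** SAP 6.3.1 analyses ACR20 at Week 12 by logistic regression with "treatment, region (Japan versus non-Japan), biologic DMARD experience (yes/no), and baseline DAS28-hsCRP as independent variables using the mITT population". Each dose is compared with placebo "using the Wald test at a 2-sided significance level of 0.05".

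SAP 6.3.3.1 carries this over to ACR50, ACR70 and ACR90: "The data in Part B will be summarized and analyzed using the same method as for the primary efficacy endpoint". For remission (DAS28-hsCRP below 2.6) and low disease activity (LDA), SAP 6.3.3.2 says that the proportions are "analyzed using method similar to the primary analysis". ACR50, ACR70, LDA and remission at Week 12 are secondary endpoints in SAP 4.2. ACR90 is exploratory under the note that closes SAP 6.3.3.1.

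SAP 6.1 has a general default, that Fisher's "exact test will be used for the analysis of categorical measures unless otherwise specified". A method is specified for these endpoints, so the default does not apply to them. The Cochran-Mantel-Haenszel tests in SAP 6.3.3.2 cover the four-category DAS28-hsCRP split and the EULAR categories, not remission as yes or no. Neither section has a rule for sparse cells or separation.

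**The concern.** The Wald test divides the estimated log odds ratio by its standard error. When an arm has no responders, the maximum likelihood estimate runs to infinity and the standard error grows faster than the estimate. The p-value then approaches 1 whatever the other arm shows. Placebo is the common reference, so one empty placebo arm disables all three dose comparisons at once.

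The stricter response levels are where an empty arm is most likely. Following the plan as written could then give a non-significant result and an unusable odds ratio for a secondary endpoint on which the arms plainly differ. Changing the test after unblinding would be a data-driven choice.

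**Working it through.** **The plan's own figure.** Inputs from SAP 5.2: 61 per arm, 2-sided alpha .05, "assuming a 30% placebo response rate", and 61 per arm is said to suffice "to detect a difference of 25% in the primary endpoint", that is 30% versus 55%. Without continuity correction:

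n = [1.96·√(2·0.425·0.575) + 0.8416·√(0.30·0.70 + 0.55·0.45)]² / 0.25² = 60.2, rounded up to 61 per arm.

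Power at 61 per arm is 80.5%, so the stated figure reproduces. By exact enumeration at 30% versus 55%, the Wald and Firth tests both have 82% power. The Wald test is sound for ACR20.

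**The zero cell.** Unadjusted, with a placebo responders and b active responders out of 61 each:

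z = [ln(b/(61−b)) − ln(a/(61−a))] / √(1/a + 1/(61−a) + 1/b + 1/(61−b)).

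At a = 0 both ln(a/(61−a)) and 1/a are unbounded. A four-arm fit with the SAP's covariates gave, for 0 versus 6, 8 and 12 responders, standard errors of about 16,750 and p = .999 for each dose. The unadjusted alternatives are:

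| Placebo vs active (of 61) | Wald | Fisher | Firth |
|---|---|---|---|
| 0 vs 6 | about 1 | .027 | .011 |
| 0 vs 8 | about 1 | .006 | .002 |
| 0 vs 10 | about 1 | .0013 | .0005 |
| 0 vs 12 | about 1 | .0003 | .0001 |

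**How often placebo is empty.** The documents give no placebo rate for ACR70, ACR90 or remission, so the rates here are assumptions. P(no responders among 61) = (1 − p)^61:

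| Assumed placebo rate | 1% | 2% | 3% | 5% | 8% | 10% |
|---|---|---|---|---|---|---|
| Chance of an empty arm | 54% | 29% | 16% | 4% | 0.6% | 0.2% |

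**Power.** Exact enumeration over two binomials of 61, unadjusted, 2-sided .05, counting a zero cell as non-significant for Wald:

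| Placebo vs active | Wald | Fisher | Firth |
|---|---|---|---|
| 2% vs 12% | 24% | 44% | 56% |
| 3% vs 15% | 44% | 53% | 64% |
| 5% vs 18% | 54% | 52% | 62% |
| 8% vs 22% | 57% | 50% | 58% |
| 10% vs 30% | 80% | 74% | 80% |

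A covariate-adjusted four-arm simulation (1,000 trials per scenario, no covariate effect assumed) agrees: Wald 24% and Firth 59% at 2% vs 12%, and 45% and 65% at 3% vs 15%.

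**Where the loss arises.** With an empty placebo arm, Firth is significant from 5 active responders (p = .024) and Wald never is. The zero cell's share of the gap is therefore P(placebo = 0) × P(active ≥ 5):

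- 2% vs 12%: 0.292 × 0.87 = 25 points, out of a gap of 56.2 − 24.4 = 32.
- 3% vs 15%: 0.156 × 0.96 = 15 points, out of 64.1 − 43.6 = 20.5.

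Once placebo has a responder, the tests are close. The smallest number of active responders that reaches p < .05 is:

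| Placebo responders | Wald | Fisher | Firth |
|---|---|---|---|
| 1 | 8 | 8 | 7 |
| 2 | 9 | 10 | 9 |
| 3 | 11 | 11 | 10 |
| 4 | 12 | 13 | 12 |

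**Type I error.** For Firth it is at most 2.7% at common response rates of 1% to 5%.

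**The case against.** The strongest reply is that the problem depends on rates the documents do not give. At a placebo rate of 8% to 10% an empty arm is very unlikely and Wald matches Firth. At 5% versus 18% Wald is slightly above Fisher. The affected endpoints are not powered, counts and percentages are reported by arm so 0 versus 10 would be visible, and the error creates no false positives. All of this stands and limits the size of the point. It does not remove it, because nothing in the plan says what to do when the case occurs. Low rates are also plausible: 30% is assumed for the much easier ACR20, biologic-naive subjects are capped at about 25%, and discontinued subjects count as nonresponders.

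A reader might infer more than the documents support:

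- **That Wald is very conservative whenever responders are few.** The minimum counts above show otherwise. Given at least one placebo responder, Wald has more power than Fisher at 3% versus 15% (52% against 46%).
- **That these endpoints drive a go/no-go decision.** SAP 6.6 ties the interim efficacy analysis to internal planning of future studies and does not name ACR70, ACR90 or remission.
- **That the Wald test is literally prescribed for remission.** SAP 6.3.3.2 asks for a similar method. The same test is the natural reading, but not a stated one.

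**Conclusion.** The point holds as a gap in the analysis rules for ACR70, ACR90 and, on the natural reading, remission. If placebo has no responders, the specified test returns p of about 1 for all three doses whatever the difference.

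How much this matters depends on placebo rates that have to be assumed. The power loss against Firth is about 20 points at 3% versus 15% and about 32 at 2% versus 12%, mostly from the zero cell. It is 8 points at 5% versus 18% and negligible from about 8% upward. These figures are exact but unadjusted; the adjusted simulation gives the same picture.

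It would go too far to say that a real effect on these endpoints will be missed: that outcome is built in only when placebo has no responders. The error is conservative, and the ACR20 analysis and its sample size are unaffected. The gap is worth closing in the SAP, but it does not threaten the trial's main conclusion.

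**What to change.** Add one rule to SAP 6.3.3.1 and 6.3.3.2 for all secondary and exploratory binary responder endpoints (ACR50, ACR70, ACR90, LDA and remission). If any arm has fewer than 5 responders at the analysed time point, use Firth penalised-likelihood logistic regression with the same covariates, with profile penalised-likelihood tests and confidence intervals. Otherwise keep the Wald model. State in SAP 6.3.3.2 that remission and LDA use the logistic model of SAP 6.3.1 subject to this rule, so that the method no longer has to be inferred. The threshold of 5 is a choice; what matters is that it is fixed before unblinding.

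Fisher's exact test, already the SAP's general default for categorical measures, would also repair the zero cell, but it drops the covariates and has less power than Firth in the scenarios shown.

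The cost is a sentence in each section and a standard software option. The downside is that the estimation method may differ between endpoints, so the tables should label which one was used.

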6.3.3.2. DAS28-hsCRP

The DAS28-hsCRP is a measure of RA disease activity in 28 joints that consists of a composite numerical score of the following variables: TJC, SJC, hsCRP (mg/L), and the Patient's Global Assessment of Disease Activity (Vander Cruyssen et al. 2005).

$$DAS28 - hsCRP = 0.56(\sqrt{TJC28}) + 0.28(\sqrt{SJC28}) + 0.36[\ln(CRP + 1)] + 0.014(VAS) + 0.96$$

DAS28-hsCRP will be summarized by treatment at each postbaseline visit. If hsCRP is missing at a postbaseline visit, the previous postbaseline hsCRP value will be carried forward and will be used to calculate DAS28-hsCRP. The change from baseline in DAS28-hsCRP to each scheduled postbaseline time point in Part B will be analyzed by the MMRM ANCOVA. Baseline, treatment, region (Japan versus non-Japan), week of treatment (categorical), the interaction of treatment and week, biologic DMARD experience (yes/no), and baseline DAS28-hsCRP are fixed effects; subjects and error are random effects.

Subjects with DAS28-hsCRP <2.6 will be considered as having achieved clinical remission; the criterion for achieving low disease activity (LDA) will be DAS28-hsCRP ≤3.2. The number and percentage of subjects who achieve clinical remission or LDA overtime will be summarized separately and analyzed using method similar to the primary analysis.

The number and percentage of subjects with DAS28-hsCRP <2.6, ≥2.6 to ≤3.2, >3.2 to ≤5.1, >5.1 in Part B will also be summarized. The treatment group difference compare to placebo will be assessed using a Cochran-Mantel-Haenszel test, adjusting for biologic DMARD experience (yes/no), and baseline DAS28-hsCRP category (≤5.1/>5.1).

Assessments of subjects with RA by EULAR response criteria (Table JPDA.6.3) will be used to categorize subjects as nonresponders, moderate responders, good responders, or responders (moderate + good responders) according to van Gestel et al. 1998.

The number and percentage of Part B subjects in each category [nonresponders, moderate responders, good responders, or responders (moderate + good responders)] will be summarized. The treatment group will be compared to placebo using a Cochran-Mantel-Haenszel test, adjusting for biologic DMARD experience (yes/no), and baseline DAS28-hsCRP category (≤5.1/>5.1).

Table JPDA.6.3. European League Against Rheumatism Response Criteria

Postbaseline level of DAS28-hsCRP	DAS28-hsCRP improvement		
	>1.2	>0.6 and ≤1.2	≤0.6
≤3.2	Good Response	Moderate Response	No Response
>3.2 and ≤5.1	Moderate Response	Moderate Response	No Response
>5.1	Moderate Response	No Response	No Response

Abbreviations: DAS28 = Disease Activity Score modified to include the 28 diarthrodial joint count;
hsCRP = high-sensitivity C-reactive protein.

